Table 7-2:	IMP doses to be administered (equivalent to approximately [REDACTED] by body weight.....	45
Table 7-3:	Permitted concomitant medications	48
Table 9-4:	Infusion-related reaction grading according to the NCI Common Terminology Criteria for adverse events version 5.0 (Jun 2017)	73
Table 9-5:	Laboratory measurements	76
Table 9-6:	Required investigations and follow up for PDILI.....	78
Table 9-7:	PDILI laboratory measurements.....	82
Table 9-8:	PDILI information to be collected	83
Table 11-1:	Serial blood sampling for rozanolixizumab concentration	90
Table 18-1:	Suggested management guidelines for infusion reactions	102

This document cannot be used to support any marketing application and any extensions or variations thereto

LIST OF ABBREVIATIONS

ADA	antidrug antibody
ADL	activities of daily living
AE	adverse event
ALP	alkaline phosphatase
ALT	alanine aminotransferase
AST	aspartate aminotransferase
AUC	area under the curve from time 0 to infinity
BP	blood pressure
CDMS	clinical data management system
CI	confidence interval
CIDP	chronic inflammatory demyelinating polyradiculoneuropathy
C _{max}	maximum observed plasma concentration
CRO	contract research organization
C-SSRS	Columbia Suicide Severity Rating Scale
CTCAE	Common Terminology Criteria for Adverse Events
DMC	Data Monitoring Committee
ECG	electrocardiogram
eCRF	electronic Case Report form
ES	Enrolled Set
EudraCT	European Union Drug Regulating Authorities Clinical Trials
FAS	Full Analysis Set
FcRn	neonatal Fc receptor
FIH	first-in-human
FV	Final Visit
GCP	Good Clinical Practice
HIV	human immunodeficiency virus
HIV1	human immunodeficiency virus antibody 1
HIV2	human immunodeficiency virus antibody 2
IA	immunoabsorption
IB	Investigator's Brochure
ICF	Informed Consent form

ICH	International Council for Harmonisation
IEC	Independent Ethics Committee
IgA	immunoglobulin A
IgE	immunoglobulin E
IgG	immunoglobulin G
IgM	immunoglobulin M
IGRA	interferon gamma release assay
IMP	investigational medicinal product
INCAT	Inflammatory Neuropathy Cause and Treatment
IND	Investigational New Drug
IRB	Institutional Review Board
iRODS	inflammatory Rasch-built Overall Disability Scale
IRT	interactive response technology
ITP	immune thrombocytopenia
iv	intravenous(ly)
IVIg	intravenous immunoglobulin
LLOQ	lower limit of quantification
logit	log odds unit
LTBI	latent tuberculosis infection
MCID-SE	minimum clinically important differences-standard error
MedDRA	Medical Dictionary for Regulatory Activities
MG	myasthenia gravis
NF-L	neurofilament light chain
NTMBI	nontuberculosis mycobacterium infection
OLE	open-label extension
PD	pharmacodynamics
PDILI	potential drug-induced liver injury
PD-PPS	Pharmacodynamic Per-Protocol Set
PDS	Protocol Deviation Specification
PEOT	premature end of treatment
PGIC	Patient Global Impressions of Change
PGIS	Patient Global Impressions of Severity

This document cannot be used to support any application and/or extension or variations thereof.

PK	pharmacokinetic
PK-PPS	Pharmacokinetic Per-Protocol Set
PLEX	plasma exchange
PPS	Per-Protocol Set
PR	pulse rate
PRO	patient-reported outcome
PS	Patient Safety
QTc	QT-interval corrected for heart rate
RT-MRC	Rasch-built, modified interval Medical Research Council scale
SAE	serious adverse event
SAP	Statistical Analysis Plan
sc	subcutaneous(ly)
SCIg	subcutaneous immunoglobulin
SD	standard deviation
SOC	standard of care
SOP	Standard Operating Procedure
SS	Safety Set
TB	tuberculosis
TEAE	treatment-emergent adverse event
ULN	upper limit of normal
WHO	World Health Organization

This document cannot be used to support any marketing authorization application and any extensions or variations thereof.

1 SUMMARY

Rozanolixizumab (UCB7665) is a humanized anti-neonatal Fc receptor (FcRn) monoclonal antibody that is being developed as an inhibitor of FcRn activity with the aim to reduce the concentration of pathogenic immunoglobulin (IgG) in patients with IgG auto-antibody mediated diseases such as chronic inflammatory demyelinating polyradiculoneuropathy (CIDP).

CIDP04 is a Phase 2A, multicenter, single-arm, open-label study with the primary objective of evaluating the long-term safety and tolerability of rozanolixizumab when administered as [REDACTED] subcutaneous (sc) infusion in study participants with CIDP. The secondary objective includes evaluating the long-term clinical efficacy of [REDACTED] doses of rozanolixizumab in the study participants with CIDP. This open-label study will provide study participants from previous rozanolixizumab studies (eg, CIDP01) the opportunity to have continued access to rozanolixizumab.

Access to CIDP04 for study participants coming from CIPD01: Study participants from CIDP01 who have completed the Treatment Period (ie, all visits up to Visit 17) without a relapse of CIDP will be offered the opportunity to be directly enrolled into this open-label extension (OLE) study. Study participants from CIDP01 who have experienced a relapse of CIDP (during either the Treatment Period or the Observation Period) and have been successfully rescued and stabilized with standard of care (SOC) medication may also be eligible to enroll in CIDP04. The study participants who completed the Treatment Period will be offered the opportunity to enter directly once stabilized. The study participants who relapsed during Treatment Period will be offered entry into CIDP04 only once CIDP01 study results are available, after the blind has been broken at the end of the study, and it is confirmed they received placebo in CIDP01.

In case the study participants have a gap period between the end of the parent study and the start of this open-label study (ie, last visit in the parent study does not take place on the same day as entry of study CIDP04), a Screening Period of 2 to 5 weeks will be applicable to confirm that the study participant still meets the eligibility criteria for entry in the open-label study and allow for a smooth transition between the treatment used by the study participants during the gap period and initiation of rozanolixizumab. The CIDP04 study includes a 24-week Treatment Period, an optional additional maximum 52-week Treatment Period followed by an 8-week Observation Period. The length of the additional Treatment and Observation Periods may be shortened in case of availability of an Access Program. For the Treatment Periods, study participants will have weekly visits (either on site or at home) during which they will be dosed with an sc infusion of rozanolixizumab, up to [REDACTED]. The initial dose in the study will be based on the dose the study participant has received at the completion of the parent study (eg, CIDP01). For study participants who were known to be on placebo in the parent study (eg, CIDP01), a starting dose of [REDACTED] will be used. Dose may be reduced to [REDACTED] if [REDACTED] is not tolerable (eg, headache) and/or recurrent low IgG levels (Treatment Period Part 2). The maximum dose of rozanolixizumab in CIDP04 will be [REDACTED]. For exact doses to be administered, refer to Section 7.2.

The primary safety variable is the occurrence of treatment-emergent adverse events (TEAEs). The other safety variables include TEAEs leading to withdrawal of the investigational medicinal product (IMP); assessment of values and change from Baseline of: vital signs (systolic and diastolic blood pressure [BP], pulse rate [PR], body temperature, and body weight); physical and

neurological examination findings; 12-lead electrocardiograms (ECGs); clinical laboratory findings (hematology, clinical chemistry, and urinalysis); Tuberculosis Signs and Symptoms Questionnaire; and total protein, albumin, α - and β -globulins. The other variables include the efficacy variables of changes in study participant's score on inflammatory Rasch built Overall Disability Scale (iRODS), Inflammatory Neuropathy Cause and Treatment (INCAT), maximum grip strength (assessed by site personnel), the Rasch-built, modified interval Medical Research Council scale (RT-MRC) sum score, and patient-reported outcomes (PROs); pharmacokinetic (PK) variable of the plasma concentration of rozanolixizumab; pharmacodynamic (PD) variables of changes in concentration of serum IgG, and its subclasses, and neurofilament light chain (NF-L) levels in serum; and immunological variables of changes in concentration of serum IgA, IgE, and IgM, serum complement levels (C3 and C4) and plasma complement levels (C3a and C5a), anti-rozanolixizumab antibodies levels, cytokines levels, CIDP-specific auto-antibody levels, and tetanus- and influenza A virus-specific IgG antibodies.

A total of █ study participants participating in the parent study CIDP01 may be enrolled in this OLE study; enrollment is planned at approximately 24 sites in Europe, United States of America, and Canada, with possible extension to other regions and countries.

A Data Monitoring Committee (DMC) will be established for the study.

This document cannot be used to support any application and any extensions or variations of marketing authorization

2 INTRODUCTION

Chronic inflammatory demyelinating polyradiculoneuropathy is a rare disorder of the peripheral nerves characterized by chronic and progressive onset of weakness, loss of sensation, reflexes, reduction or partial block in motor nerve conduction, and often pain and imbalance. Worldwide, the prevalence of CIDP ranges from approximately 1 to 9 cases per 100,000 (Mathey et al, 2015). For many patients, CIDP results in substantial disability, limiting their activities resulting in an overall negative impact on quality of life across multiple dimensions. Progressive disease and/or relapses can result in difficulty moving arms, hands, legs, and feet, a loss in the ability to walk independently or confinement to wheelchairs and reliance on caregivers (Mahdi-Rogers et al, 2014). Healthcare costs for CIDP are substantial (Guptill et al, 2014; Mahdi-Rogers et al, 2014; Olesen et al, 2012).

Cellular and humoral immune mechanisms are thought to be involved in the pathogenesis of CIDP resulting in inflammatory lesions in the spinal roots, proximal nerve trunks and along the peripheral nerves. The essential role of the autoimmune antibodies in mediating this pathology is supported by the improvement seen after plasma exchange (PLEX) and immunoabsorption (IA). Identification of the specific antigenic target(s) of the autoimmune antibodies in CIDP is expanding with recent immunological techniques.

Although the prognosis of CIDP has markedly improved over the last decades, significant disability remains. High-dose steroids, PLEX, IA, and intravenous and subcutaneous immunoglobulin (IVIg and SC Ig) have all been shown to be effective treatments for CIDP. However, comorbid diseases, including hypertension, diabetes, and psychiatric diseases, limit the use of high-dose steroids. While PLEX is effective, the procedure is burdensome for patients. Immunoglobulin treatment (IVIg and SC Ig) is often used as first-line treatment but there remains a medical need for improved therapeutic options.

The neonatal major histocompatibility complex-class-I-like FcRn recycles immunoglobulin G (IgG) and albumin from most cells and transports it bi-directionally across epithelial barriers to affect systemic and mucosal immunity. It has been shown that FcRn rescues both IgG and albumin from intracellular lysosomal degradation by recycling it from the sorting endosome to the cell surface (Anderson et al, 2006). Immunoglobulin G has a half-life of approximately 3 weeks in man. This is achieved by interaction of IgG with the receptor, FcRn. Thus in effect FcRn salvages IgG, and blockade of FcRn accelerates removal of endogenous IgG.

Rozanolixizumab is a humanized anti-FcRn monoclonal antibody that has been specifically designed to inhibit IgG binding to FcRn without inhibiting albumin binding to FcRn.

Rozanolixizumab is being developed as an inhibitor of FcRn activity with the aim to reduce the concentration of pathogenic IgG in patients with IgG auto-antibody mediated diseases.

Rozanolixizumab was derived from a rat antibody with specificity for human FcRn. To date, rozanolixizumab has been administered to healthy study participants in a completed first-in-human (FIH) study (UP0018), a completed Phase 2 study in study participants with primary immune thrombocytopenia (ITP) (TP0001, evaluating [REDACTED] by sc route across 5 cohorts), and a completed Phase 2 study in study participants with myasthenia gravis (MG) (MG0002, evaluating [REDACTED] by sc route).

Additional information on the development of rozanolixizumab can be found in the current version of the Investigator's Brochure (IB) for rozanolixizumab.

The extension of the development program of rozanolixizumab to the indication of CIDP is based on the underlying hypothesis that reducing the concentration of pathogenic IgG in patients with CIDP will improve the symptoms of CIDP and prevent its long-term progression. CIDP01 is the first study investigating this indication; it is a Phase 2A, multicenter, randomized, study participant-blind, investigator-blind, placebo-controlled, parallel-group study with the primary objective of evaluating the clinical efficacy of rozanolixizumab as a treatment for study participants with active CIDP who have been maintained on an immunoglobulin-dependent regimen. In addition, CIDP01 will assess the safety and tolerability of multiple dosing with rozanolixizumab including the development of antidrug antibodies (ADA) and potential to impact clinical response, and will provide information on the PK and PD of rozanolixizumab in study participants with active CIDP. The maximum duration of the study per study participant is approximately 28 weeks (up to maximum 40 weeks), consisting of a Screening Period of between 2 and 5 weeks duration, an 11-week Treatment Period, and an Observation Period of 12 weeks (up to 24 weeks). Study participants will be randomized to 1 of 2 treatment arms: rozanolixizumab [REDACTED] sc or placebo sc in a ratio of 1:1. Study participants will receive [REDACTED] of IMP.

2.1.1 Rationale for this study

CIDP04 will evaluate the long-term safety, tolerability, and efficacy of treatment with rozanolixizumab with a [REDACTED] dosing regimen for 24 weeks in subjects with active CIDP who have been maintained on an immunoglobulin-dependent regimen. An optional extension of the treatment period by a maximum of an additional 52 weeks, or until an Access Program or equivalent is in place, whichever comes first, will be allowed on the basis of each participant's individual benefit-risk assessment at the end of the first 24-weeks Treatment Period. Study participants may choose to self-administer the IMP during Treatment Period Part 2 under supervision of a nurse and after having received appropriate training.

The CIDP04 OLE study will provide the opportunity to assess the long-term safety of rozanolixizumab in study participants with CIDP from CIDP01.

3 STUDY OBJECTIVES

3.1 Primary objective

The primary objective of the study is to assess long-term safety and tolerability of [REDACTED] doses of rozanolixizumab in study participants with CIDP.

3.2 Secondary objective

The secondary objective of the study is to assess long-term clinical efficacy of [REDACTED] doses of rozanolixizumab.

3.3 Exploratory objectives

The exploratory objectives of the study are to assess the PD, PK, and immunological variables in the treatment course with rozanolixizumab and to assess whether long-term dosing of rozanolixizumab improves PROs. These include:

- The PD effect of rozanolixizumab as measured by the total IgG concentrations in serum

- The effects of rozanolixizumab on the concentrations of total protein, albumin, α - and β -globulins, IgG subclasses, IgM, IgA, IgE, and serum and plasma complement levels
- The incidence and emergence of ADA with respect to immunogenicity and PK and PD
- The effect of rozanolixizumab on complement and cytokines
- The plasma concentrations of rozanolixizumab administered by sc infusion
- The PD effect of rozanolixizumab as measured by NF-L in serum
- The effect of rozanolixizumab on CIDP-specific auto-antibody levels
- The effect of rozanolixizumab on vaccine antibody levels (influenza A and tetanus)
- The effect of rozanolixizumab on exploratory biomarkers, and explore the relationship between protein and metabolite biomarkers and cause, progression, and appropriate treatment of CIDP

4 STUDY VARIABLES

For all study variables, the Baseline values for study participants who enroll directly into CIDP04 will be the Baseline values from the parent study (eg, CIDP01). For study participants with a gap period prior to enrollment in CIDP04, details of the analyses of specific Baseline will be available in the Statistical Analysis Plan (SAP).

4.1 Safety variables

4.1.1 Primary safety variables

The primary safety variable is:

- Occurrence of TEAEs

4.1.2 Other safety variables

The other safety variables are:

- TEAEs leading to permanent withdrawal of IMP
- Vital signs values and changes from Baseline (systolic and diastolic BP, PR, body temperature, and body weight) at each scheduled assessment during the Treatment and Observation Periods
- Physical examination findings
- Neurological examination findings
- 12-lead ECG values and change from Baseline at each scheduled assessment during the Treatment and Observation Periods
- Laboratory values and changes from Baseline at each scheduled assessment during the Treatment and Observation Periods (hematology, clinical chemistry, and urinalysis)
- Tuberculosis Signs and Symptoms Questionnaire at each scheduled assessment during the Treatment and Observation Periods

- Values and change from Baseline in concentrations of total protein, albumin, α - and β -globulins at each scheduled assessment during the Treatment and Observation Periods

4.2 Other variables

4.2.1 Efficacy variables

Preliminary definitions linked to assessment of relapse:

- CIDP relapse (iRODS) is defined as a clinically important deterioration from Baseline in iRODS score, ie, a minimum clinically important differences-standard error (MCID-SE) of ≤ -1.96
- CIDP relapse (adjusted INCAT) is defined as an increase from Baseline of at least 1 point in the adjusted INCAT score. The adjusted score is identical to the INCAT disability score except for the exclusion of changes in upper limb function from 0 (normal) to 1 (minor symptoms) or from 1 to 0
- CIDP relapse (maximum grip strength as assessed by site personnel) is defined as a clinically important deterioration from Baseline in grip strength as measured by site personnel, ie, a decline of $>14\text{kPa}$

The other efficacy variables are:

- Values and absolute change from Baseline in iRODS scores at each scheduled assessment during the Treatment and Observation Periods
- Study participant experienced CIDP relapse (iRODS) up to Week 25 and Week 77 (where applicable) from Baseline
- Time to CIDP relapse (iRODS) during the Treatment Period from Baseline
- Study participant experienced CIDP relapse (adjusted INCAT) up to Week 25 and Week 77 (where applicable) from Baseline
- Time to CIDP relapse (adjusted INCAT) during the Treatment Periods from Baseline
- Values and absolute change from Baseline in adjusted INCAT score at each scheduled assessment during the Treatment and Observation Periods
- Study participant experienced CIDP relapse (maximum grip strength as assessed by site personnel) up to Week 25 and Week 77 (where applicable) from Baseline
- Time to CIDP relapse (maximum grip strength as assessed by site personnel) during the Treatment Periods from Baseline
- Values and absolute change from Baseline in maximum grip strength score (maximum of 3 assessments) taken by site personnel at each scheduled assessment during the Treatment and Observation Periods
- Values and absolute change from Baseline in RT-MRC sum score at each scheduled assessment during the Treatment and Observation Periods
- Study participants receiving rescue medication during Treatment Periods

- Time to rescue medication administration during Treatment Periods

4.2.2 Patient-reported outcome variables

The PRO variables are:

- Values and change from Baseline in fatigue domain scores at each scheduled assessment during the Treatment and Observation Periods
- Values and change from Baseline in CIDP PRO instrument domain scores at each scheduled assessment during the Treatment and Observation Periods
- Values and change from Baseline in Patient Global Impressions of Severity (PGIS) at each scheduled assessment during the Treatment and Observation Periods
- Patient Global Impressions of Change (PGIC) value at each scheduled assessment during the Treatment and Observations Periods

4.2.3 Pharmacokinetic variable

The PK variable is the plasma concentration of rozanolixizumab at each scheduled assessment during the Treatment Periods.

4.2.4 Pharmacodynamic variables

The PD variables are:

- Minimum value and maximum decrease (absolute and percentage) from Baseline in total serum IgG concentration during the study
- Values and change (absolute and percentage) from Baseline in total serum IgG concentrations at each scheduled assessment during Treatment and Observation Periods
- Values and change (absolute and percentage) from Baseline in serum IgG subclass concentrations at each scheduled assessment during Treatment and Observation Periods
- Values and change (absolute and percentage) from Baseline in NF-L levels at each scheduled assessment during Treatment and Observation Periods

4.2.5 Immunological variables

The immunological variables are:

- Values and change from Baseline in serum immunoglobulin concentrations (total IgA, IgE, and IgM) at each scheduled assessment during Treatment and Observation Periods
- Values and change from Baseline in serum complement levels (C3 and C4) and plasma complement levels (C3a and C5a) at each scheduled assessment during Treatment Period
- ADA (anti-rozanolixizumab antibodies) status (negative or confirmed positive) and the confirmed positive titer at each scheduled assessment during Treatment and Observation Periods
- Values and change from Baseline in cytokines at each scheduled assessment during Treatment and Observation Periods

- Change in CIDP-specific auto-antibody levels in serum from Baseline during Treatment and Observation Periods
- Values and change from Baseline in tetanus- and influenza A virus-specific IgG antibodies during Treatment and Observation Periods

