9. Study participant has active suicidal ideation as indicated by a positive response (“Yes”) to either Question 4 or Question 5 of the “Since Last Visit” version of the Columbia Suicide Severity Rating Scale (C-SSRS) at Baseline Visit (Visit 2),

or

Study participant has a lifetime history of suicide attempt (including an active attempt, interrupted attempt, or aborted attempt), or has suicidal ideation in the past 6 months as indicated by a positive response (“Yes”) to either Question 4 or Question 5 on the Screening C-SSRS.

The study participant should be referred immediately to a Mental Healthcare Professional and must be withdrawn from the study.

10. Study participant has a known hypersensitivity to any components of rozanolixizumab.
11. Study participant intends to have a live vaccination during the course of the study or within 7 weeks following the final dose of rozanolixizumab.
12. Study participant has an ongoing serious adverse event (SAE) or a medical condition in the parent study that the investigator considers to put the study participant at a significantly increased risk of participating in CIDP04.
13. Study participant has any planned elective surgery due to occur during the study dosing period which in the opinion of the investigator could interfere with study procedures.

6.2.1 Additional exclusion criteria for study participants with a gap period between the parent study and entry in CIDP04

14. Study participant has a current diagnosis or has a history of Type 1 or Type 2 diabetes mellitus and/or hemoglobin A1c level >6.0%.
15. Study participant with IgM paraproteinemia.
16. Study participant has known IgM-mediated neuropathy (eg, multifocal motor neuropathy).
17. Study participant has clinical or known evidence of associated systemic diseases that might cause neuropathy, including but not limited to connective tissue disease, Lyme disease, Castleman's disease and systemic lupus erythematosus, malignant plasma cell dysplasia, or treatment with agents that might lead to neuropathy (eg, amiodarone therapy).
18. Study participant on an average dose less than 0.4g IgG/kg/month over the past 4 months.

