7.8.2 Prohibited concomitant treatments (medications and therapies)

The following concomitant medications are prohibited during the Treatment Period:

- IVIg and SC Ig (refer to Section 7.8.3)
- All biologics including rituximab
- Cyclophosphamide
- Pimecrolimus
- IPP-201101 (Lupuzor™)
- Systemic dexamethasone
- PLEX
- IA

If a study participant requires or takes IVIg, SC Ig, PLEX, dexamethasone, or rituximab, they must be discontinued from IMP. In all other cases of intake of prohibited concomitant medication, the investigator will (where possible) discuss with the Medical Monitor and/or Sponsor Study Physician and a decision will be made whether the study participant should discontinue IMP (see Section 6.4).

If a study participant is discontinued from IMP they should be encouraged to complete Visit 26/PEOT and complete the Observation Period (see [Table 5-1](#) and Section [6.4](#)).

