 - Vaccination-specific antibody titers (tetanus and influenza Type A) (on-site visits only [Weeks 25, 37, 49, 61])
 - Immunoglobulins (total IgG and IgG subclasses)

- IgA, IgM, IgE (on-site visits only [Weeks 25, 37, 49, 61])
- NF-L (only at Week 25)
- CIDP specific auto-antibodies (only at Week 25)
- Urine pregnancy test
- Contact IRT
- Administer IMP – self-administration by the study participant under the supervision of the nurse (to confirm that study participant is proceeding correctly) may be considered provided the participant is willing to do so, the participant has been adequately trained by the site personnel according to Self-administration training guidance document
- INCAT assessment
- Assessment of grip strength by site personnel

8.3.2 Additional home visits during Treatment Period Part 2 (weekly in between site visits starting at Week 26 or until availability of an Access Program (whichever comes first)

The following procedures will be performed during the Treatment Period Part 2 by a healthcare professional visiting the study participant at his or her home. Visits will be performed weekly in between monthly site visits (Section 8.3.1):

- Withdrawal criteria assessment
- Prior and concomitant medications
- Concomitant medical procedures
- Vital signs (prior to IMP administration, at the end of the infusion)
- Recording of AEs
- Contact IRT
- Administer IMP (unless IMP is temporarily discontinued (see Section 6.4.1.3) – self-administration by the study participant under the supervision of the home nurse may be considered provided the participant is willing to do it and has been adequately trained by the site personnel according to Self-administration training guidance document.

8.4 Observation Period, Visits 26 to 29 (Weeks 25 to 32 study participants completing Treatment Period Part 1 only and Weeks 77 to 84 for study participants completing Treatment Period Part 1 and Part 2)

Following the final dose of rozanolixizumab at Week 24 (Visit 25) or Week 76, 4 subsequent visits will be scheduled over 8 weeks (Visits 26 to 29) to collect safety and efficacy data for study-related outcome measures and procedures unless the study participant continues rozanolixizumab treatment under an Access Program or equivalent. In the latter case, only the PEOT Visit (Visit 26) will be performed. Visit 27 and Visit 28 are home nursing visits to be

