4.2.4 Immunological data

The rules for handling BLQ or ALQ measurements for all immunological data will be as described in [Section 4.2.2](#).

Descriptive statistics will be calculated if at most 33% of the individual data points at a timepoint are missing or are either not quantifiable (<LLOQ) or ALQ as described in [Section 4.2.2](#).

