9.3 Immunological analyses

All analyses described in this section will be based on the SS.

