9.3.6 Tetanus-and influenza A virus-specific IgG antibodies

Tetanus-and influenza A virus-specific IgG antibodies will be listed by treatment group and time point. Summaries using descriptive statistics will be presented by treatment group and time point for both absolute values and changes from Baseline.

Any values are that BLQ or ALQ will be handled as described in [Section 4.2.4](#).

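### SAP 9.3.6 has no rule for tetanus or influenza A titres drawn after an on-study vaccination against the same antigen, so the change summary could understate the fall it is meant to describe

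*Protocol*

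**What the plan says.** - **Objective.** Protocol 3.3 lists as exploratory "The effect of rozanolixizumab on vaccine antibody levels (influenza A and tetanus".
- **Variable.** Protocol 4.2.5: "Values and change from Baseline in tetanus- and influenza A virus-specific IgG antibodies during Treatment and Observation Periods", with no condition on vaccination.
- **Analysis.** SAP 9.3.6: "Summaries using descriptive statistics will be presented by treatment group and time point for both absolute values and changes from Baseline". SAP 9.3 sets the population: "All analyses described in this section will be based on the SS".
- **Data handling.** The rules specific to these data are in SAP 4.2.4: "The rules for handling BLQ or ALQ measurements for all immunological data will be as described in" SAP 4.2.2. The same section says descriptive statistics are given only if at most 33% of data points at a timepoint are missing or not quantifiable.
- **Vaccination.** Exclusion criterion 11 in Protocol 6.2 reads "Study participant intends to have a live vaccination during the course of the study or within 7 weeks following the final dose of rozanolixizumab". Criterion 24, for participants with a gap period, also concerns live vaccines only. Protocol 7.8.2 opens "The following concomitant medications are prohibited during the Treatment Period", and the list that follows names no vaccine.
- **Sampling.** Titres are drawn at Screening, Visit 8 (Week 7), Visit 14 (Week 13) and Visit 26 (Week 25, Week 77 or early end of treatment). For Part 2, Protocol 8.3.1 adds "Vaccination-specific antibody titers (tetanus and influenza Type A) (on-site visits only [Weeks 25, 37, 49, 61".
- **Baseline.** Under SAP Table 3-1, Baseline for these antibodies is the parent-study Screening visit for previously treated participants. For those who had placebo it is the CIDP04 Screening visit, where there was one.

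**The concern.** A vaccination against tetanus or influenza A is intended to raise the antibody being measured, while the drug is expected to lower it. The study has one arm, so no concurrent control separates the two effects. A boosted titre that enters the mean pulls the summary towards no loss, which is the reassuring direction for a safety-relevant question.

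The SAP already applies the underlying principle elsewhere. SAP 3.9 treats efficacy assessments after rescue medication as invalid, to prevent bias. SAP 10.2 splits Observation Period adverse events by receipt of standard-of-care immunoglobulin, identified by drug code. Vaccination against the measured antigen has no comparable rule.

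**Working it through.** **1. Can a post-vaccination titre occur?** Non-live vaccines are not excluded. Protocol 7.8.2 prohibits all biologics, but Protocol Table 6-1 glosses that term as monoclonal antibodies and fusion proteins, and a live-vaccine criterion stands separately. Week 1 to Week 61 is 60 weeks, so a participant sampled then has passed through every calendar season. For a previously treated direct entrant, Baseline is earlier by the parent study's 2- to 5-week Screening and 11-week Treatment Period (Protocol 2). The interval is then about 2 + 11 + 60 = 73 to 5 + 11 + 60 = 76 weeks.

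**2. Would the plan remove or separate it?** No. The analysis set is the Safety Set, so there is no per-protocol exclusion. SAP 4.2.4 concerns quantification limits and missing data only. The invalid-value rule in SAP 3.9 covers efficacy only.

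**3. How large could the effect be?** The plan gives no figure to reproduce: no expected fall, spread, vaccination frequency or boost. All three inputs below are therefore assumptions, shown over a range:

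- r = true fall in specific IgG, 30% to 70%
- b = titre after vaccination as a multiple of the reduced level, 2 to 8
- f = share of participants vaccinated before the sample, 10% to 50%

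With Baseline set to 1 and the boost fully present at sampling:

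- mean change = (1 - r) × [1 + f(b - 1)] - 1
- share at which the mean fall disappears: f* = r / [(1 - r)(b - 1)]

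For r = 50%, b = 4, f = 25%: 0.5 × (1 + 0.25 × 3) - 1 = -12.5%, and f* = 0.5 / (0.5 × 3) = 33%.

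| r | b | f = 10% | f = 25% | f = 50% | f* |
|---|---|---|---|---|---|
| 30% | 2 | -23.0% | -12.5% | +5.0% | 43% |
| 30% | 4 | -9.0% | +22.5% | +75.0% | 14% |
| 30% | 8 | +19.0% | +92.5% | +215.0% | 6% |
| 50% | 2 | -45.0% | -37.5% | -25.0% | 100% |
| 50% | 4 | -35.0% | -12.5% | +25.0% | 33% |
| 50% | 8 | -15.0% | +37.5% | +125.0% | 14% |
| 70% | 2 | -67.0% | -62.5% | -55.0% | not reachable |
| 70% | 4 | -61.0% | -47.5% | -25.0% | 78% |
| 70% | 8 | -49.0% | -17.5% | +35.0% | 33% |

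At f = 0 the mean change equals -r.

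**4. What would the median show?** SAP 3.1 also reports the median, minimum and maximum. For r = 50%, b = 4 and an assumed log-normal spread (log-SD 0.5), simulation gives a median change of about -56% at f = 0, -53% at 10%, -46% at 25% and -12% at 50%. The mean moves from -50% to -12.5% by f = 25%; the median moves about 10 percentage points.

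**5. Would simple exclusion work under the present rules?** If excluded values counted as missing under SAP 4.2.4, any visit with more than 33% excluded would show no statistics. The visits most affected by vaccination would then be blank.

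**The case against.** The strongest reply is that the objective speaks of vaccine antibody levels, and neither existing nor protective antibody is mentioned. Describing the levels participants actually have on long-term treatment, vaccinations included, is a legitimate reading. That stands, and it is why the all-values summary should stay.

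A reader might infer that the table hides the loss, or that the mean must understate it. The documents support neither:

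- They give no vaccination frequency, boost size or expected fall, and nothing at all on how often tetanus vaccination would occur.
- The 76 weeks of treatment is a maximum. Part 2 is optional and may be shortened, and a 24-week participant need not meet an influenza season.
- The median, minimum and maximum are reported, titres are listed individually (SAP 9.3.6), and concomitant medications are listed with dates (SAP 6.4).
- The calculation assumes the boost is fully present at sampling. Protocol 2 says FcRn blockade speeds IgG removal, and Part 2 samples are 12 weeks apart, so a boost may have partly faded.
- Net direction is not established. Participants with a gap period enter on stable immunoglobulin (inclusion criterion 6), which is then prohibited. If therapeutic immunoglobulin carries these antibodies, which the documents do not say, stopping it would exaggerate the fall, and rescue or a return to it would raise titres.

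So an extra summary would remove one influence without isolating the drug effect. The gap remains: to interpret the planned table, a reader would have to match two listings by hand.

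**Conclusion.** The concern holds as a limited point. SAP 9.3.6 has no rule for titres drawn after a matching on-study vaccination, such vaccination is not barred, and sampling can span more than a year. Taken alone, those values could attenuate the apparent fall and, if vaccination is common, mask it.

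The size is unknown. Under the assumed ranges it runs from a shift of 3 percentage points in the mean (-70% to -67% at r = 70%, b = 2, f = 10%) to a reversed sign. The median is more robust in the case simulated. The documents do not support saying that the loss is in fact hidden, or that the overall bias has a known direction.

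The variable is exploratory and descriptive, and no sample size rests on it. The IgG-based interruption rules in Protocol 6.4.1 use total IgG, not these titres. This is a cheap improvement, not a flaw in the trial's main conclusions.

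**What to change.** In SAP 9.3.6:

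- Keep the summary of all values.
- Add a by-visit summary that excludes influenza A values after any influenza vaccination, and tetanus values after any tetanus-containing vaccination.
- Identify vaccinations from recorded concomitant medication since the participant's own Baseline. For previously treated participants this must include parent-study records, because their Baseline lies there and SAP 6.4.1 defines no prior medications for direct entrants. Confirm that vaccinations are recorded as concomitant medication; the documents do not say so explicitly.
- Show the number excluded at each visit.
- State that excluded values do not count as missing under the 33% rule in SAP 4.2.4.
- Flag them in the titre listing.

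The cost is a short SAP addition, one flag derived from existing data and one extra table. The added summary will have fewer values at late visits, and it conditions on a post-Baseline event, so it should be read beside the all-values table and not in place of it. No change to trial conduct is needed.
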